beforehand and given suitable personal protection equipment (i.e. universal blood and body fluid precautions - especially when handling ashes containing potentially radioactive bone fragments. Calculations and the rationale for radiation dose estimates are available upon request (see investigators Brochure).

Definition of Dose-Limiting Toxicities (DLTs):

Toxicities will be graded in severity according to the guidelines outlined in the NCI Common Terminology Criteria for Adverse Events (CTCAE) version 4.0 (publish date 28-May-2009). Dose-limiting toxicities include all adverse experiences that are related to study medication, and clearly not related to disease progression or intercurrent illness.

Based on prior experience with other bone seeking radiopharmaceuticals and Ra-223 dichloride in prostate cancer patients, the expected dose limiting toxicity (DLT) will be hematologic. Lymphopenia is common in patients with bone metastases and will be monitored, but not considered a DLT in this protocol. Any grade 4 anemia, any grade 4 neutropenia for >7 days or grade 4 neutropenia with fever (a single temperature greater than 38.3°C or a sustained temperature of $\geq 38^\circ\text{C}$ for more than one hour) and grade 3 or 4 thrombocytopenia with clinically significant bleeding will be dose limiting. Grade 3 non-hematologic toxicities except for nausea, emesis or diarrhea that are controlled with maximal medical management within 72 hours will be considered dose-limiting. DLTs will only be monitored during the first 6 weeks of treatment. Ongoing toxicity that causes a delay of more than 2 weeks in starting the next cycle will also be dose-limiting if it occurs during the first cycle.

Dose Modification and Escalation

Every effort should be made to administer the full dosing regimen of Ra-223 dichloride. Adjustment of dose level is not permitted.

- A minimum of 3 patients initially will be enrolled at the first dose level.
- If at least 2 patients are observed to have a dose-limiting toxicity (DLT), the MTD will have been exceeded and no further patients will be enrolled at this dose level or at any higher dose level. The prior dose level is defined as the MTD (unless only 3 patients have been treated at that level, in which case it is the tentative MTD).
- If 0 of the 3 patients are observed to have DLT during the DLT assessment period, the dose level is escalated one step for the next cohort of 3 patients, and the process continues as above.

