- If exactly 1 of the 3 patients treated show DLT during the DLT assessment period, 3 additional patients are treated at the current dose level.
- If none of these additional 3 patients show DLT during the DLT assessment period, the dose level is escalated for the next cohort of 3 patients, and the process continues as above; otherwise, the prior dose level is defined as the MTD (unless only 3 patients have been treated at that level, in which case it is the tentative MTD).
- A tentative MTD becomes final when a total of 6 patients are treated with less than 2 showing DLT.
- If 2 of the first 3 patients have hematologic DLT, then next cohort will be dose level -1.

Study visits during the treatment period should occur at 4 weeks intervals (within a window of +/- 7 days). **Dosing delays** may be instituted under the following circumstances:

Disease progression:

The Investigator should delay cytotoxic chemotherapy, other systemic radioisotope, hemibody external radiotherapy or other investigational drug until the follow-up period. If such treatments have to be given during the treatment period, further study drug administrations must be discontinued. Patients with disease progression may continue other treatment at the Investigator's discretion.

Myelosuppression:

Treatment-related changes in hematology parameters may occur.

- Blood transfusion is acceptable between study drug administrations. Use of biologic response modifiers, such as G-CSF or GM-CSF, is allowed in the management of acute toxicity.
- If myeloid growth factors are required for the management of acute toxicity this event should be considered a DLT.

Gastrointestinal events:

Diarrhea should be treated as per local practice. A further dose of study medication should not be given before diarrhea is recovered to CTCAE v4.03 Grade 2 or baseline levels.

Nausea or vomiting should be treated as per local practice. A further dose of study medication should not be given before nausea or vomiting is recovered to CTCAE v.4.03 Grade 2 or baseline levels.

For any grade 3 hematologic toxicity for >14 days, study drug administrations must be discontinued (grade 4 events of anemia and neutropenia >7 days are dose-limiting).

Spinal Cord Compression:

If the patient experiences spinal cord compression during the treatment period, the patient should be treated for the event, and this will be considered disease progression.

Surgical Intervention:

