6.5 Prior and concomitant therapy-

During treatment, all concomitant medications (including start/stop dates and indication) must be recorded in the patient's medical record and case report form (DMI)

Permitted

- Treatment with non-conventional therapies (e.g., herbs [with the exception of St. John’s Wart], acupuncture) and vitamin/mineral supplements is acceptable provided that, in the opinion of the investigator, such treatment will not interfere with the trial endpoints.
- Subjects may receive standard of care for any underlying illness.
- In the event of neutropenia, anemia, or thrombocytopenia, subjects may receive appropriate supportive care (e.g., transfusion, biologic response

modifiers such as G-CSF or GM-CSF, prophylactic antibiotics, antifungals and/or antivirals, hematopoietic growth factors). This supportive care should not substitute a recommended dose modification.

- Blood transfusions and erythropoietin are allowed during the study period
- If surgery is required during study drug treatment, the surgeon needs to be notified that the patient has been treated with a radioactive product and adequate precautions for radioactive protection should be applied during the surgical procedure. The patient should continue with study treatment if considered safe in the treating Investigator's opinion.

7. Procedures and variables

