7.1 Schedule of procedures

Labs and imaging are to be done no more than 28 days prior to registration and <30 days before dose#1 of study drug.

CBC every 2 weeks for the first 2 cycles (± 7 days), then monthly or more frequently as clinically indicated. Monitoring of hematologic toxicity will be done with monthly cbc from that point on. Weekly testing will be recommended for any patients on a clinically indicated basis if they have symptoms suggesting anemia (e.g. increased fatigue or headaches), thrombocytopenia (e.g. petechiae, bruising) or neutropenia (fevers or infection). If clinically indicated (e.g. grade 3 or higher anemia, neutropenia or thrombocytopenia, hematologic monitoring may be done more frequently.

Alkaline phosphatase will be monitored monthly. Laboratory monitoring and imaging are summarized in table 4.

Blood counts may be done by local physician as clinically indicated and also week before anticipated dosing and communicated to study team to make sure patient is ready for dosing prior to travel to MD Anderson Cancer Center.

Pregnancy test will be required when applicable prior to every cycle.

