7.4.1.2.2 Intensity

The intensity of the AE is classified according to the CTCAEv4.0. Grade refers to the severity (intensity) of the AE:

CTCAEv4 Grade 3: Severe or medically significant but not immediately life threatening; hospitalization or prolongation of hospitalization is indicated; disabling; limiting to self care ADL (self care ADL refers to bathing, dressing and undressing, feeding self, using the toilet, taking medications, and not bedridden).

CTCAEv4 Grade 4: life-threatening consequences; urgent intervention is indicated.

CTCAEv4 Grade 5: death due to an AE.

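### The dose-delay text can be read as adding a 7-day condition to grade 4 anemia that the DLT definition does not have

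*Combined protocol and SAP*

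**What the plan says.** Two places in section 6.2.9 speak to when anemia is dose-limiting.

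- **Definition of Dose-Limiting Toxicities.** The hematologic criteria begin "Any grade 4 anemia, any grade 4 neutropenia for >7 days or grade 4 neutropenia with fever". Anemia carries no duration; the 7-day condition belongs to neutropenia. A further route is open to any toxicity: "Ongoing toxicity that causes a delay of more than 2 weeks in starting the next cycle will also be dose-limiting", provided it occurs in the first cycle. The assessment window is stated as "DLTs will only be monitored during the first 6 weeks of treatment".
- **Dose Modification and Escalation, dosing delays.** A sentence on stopping study drug for grade 3 hematologic toxicity lasting more than 14 days ends with a parenthesis: "grade 4 events of anemia and neutropenia >7 days are dose-limiting".

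Transfusion is permitted in both places that deal with supportive care: "Blood transfusion is acceptable between study drug administrations" (Myelosuppression, section 6.2.9) and "Blood transfusions and erythropoietin are allowed during the study period" (section 6.5). Neither says how a transfusion affects the duration of anemia for DLT scoring. Section 7.4.1.2.2 describes the grade in these terms: "CTCAEv4 Grade 4: life-threatening consequences; urgent intervention is indicated".

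**The concern.** The parenthesis names anemia and neutropenia together and then gives one duration. It follows a clause that sets a duration for grade 3 hematologic toxicity as a whole, which makes it natural to read the 7 days as covering both grade 4 events. On that reading a related grade 4 anemia corrected within a week is not a DLT by grade. On the definition's wording it is.

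The protocol expects the DLT to be hematologic and permits transfusion, so a grade 4 anemia that is treated promptly is a case the rule has to classify. The primary objective is the maximum tolerated or recommended dose, found with cohorts of three. If two assessors apply different readings, the same patient data can lead to different escalation decisions.

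**Working it through.** **1. The texts side by side**

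| Event | DLT definition | Parenthesis, reading A: anemia; and neutropenia >7 days | Parenthesis, reading B: (anemia and neutropenia) >7 days |
|---|---|---|---|
| Grade 4 anemia, 7 days or less | DLT | DLT | Not a DLT by grade |
| Grade 4 anemia, more than 7 days | DLT | DLT | DLT |
| First-cycle delay of more than 2 weeks due to ongoing toxicity | DLT | DLT (delay rule) | DLT (delay rule) |

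Reading A agrees with the definition throughout. Reading B departs from it in the first row only.

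**2. Effect on a single cohort**

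Under the escalation rules, 0 of 3 leads to escalation, 1 of 3 leads to three more patients, and 2 or more means the MTD is exceeded. Moving one patient from DLT to no DLT turns 1/3 (add three) into 0/3 (escalate), or 2/3 (MTD exceeded) into 1/3 (add three).

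**3. Illustration of size**

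The plan has no figure to reproduce here. It states no DLT rate, no grade 4 anemia rate and no duration of anemia, so every rate below is an assumption.

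- b = rate of all other DLTs, set at 10%
- a = rate of related grade 4 anemia of any duration: 5%, 10%, 20%
- f = share of that anemia lasting more than 7 days: 0, 0.25, 0.5
- The two kinds of event are taken as independent.

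DLT rate per patient:

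- any duration counts: p = 1 − (1 − b)(1 − a)
- more than 7 days required: p = 1 − (1 − b)(1 − a·f)

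Chance of escalating past a dose, with q = 1 − p:

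P = q³ + 3pq² · q³

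Example with a = 10% and f = 0.5:

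- Any duration: p = 1 − 0.90 × 0.90 = 0.19, so P = 0.81³ + 3 × 0.19 × 0.81⁵ = 0.531 + 0.199 = 0.730.
- More than 7 days: p = 1 − 0.90 × 0.95 = 0.145, so P = 0.855³ + 3 × 0.145 × 0.855⁵ = 0.625 + 0.199 = 0.824.

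| a | P, any duration | P, >7 days, f = 0.5 | f = 0.25 | f = 0 | Increase |
|---|---|---|---|---|---|
| 5% | 0.824 | 0.867 | 0.887 | 0.906 | 0.043 to 0.082 |
| 10% | 0.730 | 0.824 | 0.867 | 0.906 | 0.094 to 0.176 |
| 20% | 0.536 | 0.730 | 0.824 | 0.906 | 0.194 to 0.370 |

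Over a wider grid (b from 5% to 20%, a from 5% to 30%, f from 0 to 0.5) the increase runs from 0.035 to 0.549. It is always towards escalation. The calculation leaves out the delay route, which would count some shorter anemias under reading B as well and so narrow the gap.

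**4. Whether duration would be observed**

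Section 7.1 schedules "CBC every 2 weeks for the first 2 cycles", with a window of 7 days either way and more frequent counts where clinically indicated. If one scheduled count shows grade 4 and the next, two weeks later, does not, the scheduled counts alone do not tell whether the event passed 7 days. Reading B would therefore also depend on unscheduled counts.

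**The case against.** The strongest reply is that the DLT definition governs. It stands under its own heading, it is clear, and an assessor scoring a DLT would go there. The parenthesis is an aside to a different rule, on stopping drug for prolonged grade 3 toxicity, and reading A makes it agree with the definition. This stands in part: it is why the point is an ambiguity and not a proven contradiction. It does not dispose of the matter, because the same dose-delay text holds an operative DLT rule that the definition lacks, namely that an event requiring myeloid growth factors is to be considered a DLT. An assessor must use both places, and nothing says which prevails.

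It can also be said that the parenthesis omits febrile neutropenia and thrombocytopenia with bleeding, so it is plainly not a restatement of the definition. That is fair. It does not claim to be complete, and the omission is not counted against it here.

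Finally, the documents give little reason to expect much grade 4 anemia. Section 1.3.2 reports anemia of all grades at 27% in both arms of the phase III prostate cancer trial, and section 4 reports no significant effects on blood counts at 50 kBq/kg. This limits confidence in the higher assumed rates. Those data come from another disease and do not cover 75 or 100 kBq/kg, so they do not settle the rate in this trial either.

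**Conclusion.** The point holds as an ambiguity in a threshold that feeds the primary objective. It can decide whether a promptly corrected grade 4 anemia is scored as a DLT, and one such patient can change a cohort decision. With 10% other DLTs, the choice of reading moves the chance of escalating by 0.04 to 0.08 at 5% grade 4 anemia, 0.09 to 0.18 at 10% and 0.19 to 0.37 at 20%. These sizes rest wholly on assumed rates, and the true size is unknown.

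Three stronger conclusions might be inferred and are not supported:

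- **That anemia could not be a DLT at all under the 7-day reading.** Grade 4 anemia lasting more than 7 days would still count, and so would a first-cycle delay of more than 2 weeks.
- **That transfusion means grade 4 anemia will hardly ever last 7 days.** The documents permit transfusion but give no correction rate or duration.
- **That escalation becomes certain.** A probability of 1.00 follows only if anemia is the sole DLT, every case resolves within 7 days and none delays the next cycle.

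**What to change.** Reconcile the DLT definition and the dosing-delay parenthesis so that a single wording states whether a duration condition applies to grade 4 anemia, and use that wording, or a reference to it, in both places. If the sponsor's rule includes a duration, the same sentence should say how duration is established and how transfusion bears on it. Which rule applies is the sponsor's decision; none is proposed here. The cost is one sentence in an amendment. It alters neither the sample size nor the escalation scheme.

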6.3 Drug logistics and accountability

All study drugs will be stored at the investigational site in accordance with Good Clinical Practice (GCP) and Good Manufacturing Practices (GMP) requirements and the instructions given by the clinical supplies department of the Institution and will be inaccessible to unauthorized personnel.

6.3.1 Accountability

The investigator, or a responsible party designated by the investigator, must maintain a careful record of the inventory and disposition of the agent (investigational or free of charge) using the NCI Drug Accountability Record or another comparable drug accountability form. (See the CTEP website at <http://ctep.cancer.gov/protocolDevelopment> for the “Policy and Guidelines for Accountability and Storage of Investigational Agents” or to obtain a copy of the drug accountability form.)

6.3.2 Destruction and Return

At the end of the study, unused supplies of alpharadin should be destroyed according to institutional policies. Destruction will be documented in the Drug Accountability Record Form. The certificate of destruction should be sent to Bayer.

6.4 Treatment compliance

An adequate record of receipt, distribution, and return of all study drugs must be kept in the form of a Drug Accountability Form.

Subject compliance with the treatment and protocol includes willingness to comply with all aspects of the protocol, and to have blood collected for all safety evaluations. At the discretion of the principal investigator, a subject may be discontinued from the trial for non-compliance with follow-up visits or study drug.

6.5 Prior and concomitant therapy-

During treatment, all concomitant medications (including start/stop dates and indication) must be recorded in the patient's medical record and case report form (DMI)

Permitted

- Treatment with non-conventional therapies (e.g., herbs [with the exception of St. John’s Wart], acupuncture) and vitamin/mineral supplements is acceptable provided that, in the opinion of the investigator, such treatment will not interfere with the trial endpoints.
- Subjects may receive standard of care for any underlying illness.
- In the event of neutropenia, anemia, or thrombocytopenia, subjects may receive appropriate supportive care (e.g., transfusion, biologic response

modifiers such as G-CSF or GM-CSF, prophylactic antibiotics, antifungals and/or antivirals, hematopoietic growth factors). This supportive care should not substitute a recommended dose modification.

- Blood transfusions and erythropoietin are allowed during the study period
- If surgery is required during study drug treatment, the surgeon needs to be notified that the patient has been treated with a radioactive product and adequate precautions for radioactive protection should be applied during the surgical procedure. The patient should continue with study treatment if considered safe in the treating Investigator's opinion.

7. Procedures and variables

7.1 Schedule of procedures

Labs and imaging are to be done no more than 28 days prior to registration and <30 days before dose#1 of study drug.

CBC every 2 weeks for the first 2 cycles (± 7 days), then monthly or more frequently as clinically indicated. Monitoring of hematologic toxicity will be done with monthly cbc from that point on. Weekly testing will be recommended for any patients on a clinically indicated basis if they have symptoms suggesting anemia (e.g. increased fatigue or headaches), thrombocytopenia (e.g. petechiae, bruising) or neutropenia (fevers or infection). If clinically indicated (e.g. grade 3 or higher anemia, neutropenia or thrombocytopenia, hematologic monitoring may be done more frequently.

Alkaline phosphatase will be monitored monthly. Laboratory monitoring and imaging are summarized in table 4.

Blood counts may be done by local physician as clinically indicated and also week before anticipated dosing and communicated to study team to make sure patient is ready for dosing prior to travel to MD Anderson Cancer Center.

Pregnancy test will be required when applicable prior to every cycle.

7.1.1 Tabulated overview

Table 4 summarizes required labs and imaging.

Table 4: **Ra-223 dichloride for Osteosarcoma: observations/monitoring**

Test/Procedure	Before entry	Doses 2-6	After dose 3+ imaging	1 month after dose (end of study± 7 days)
-----------------------	---------------------	------------------	----------------------------------	---

Physical exam (including vital signs and performance status+BPS [§])	X	X		X
CT/MRI Scans ⁺	X		X	X
Nuclear Scans*	X		X	X
CBC** w diff	X	X	X	X
Creatinine	X		X	X
Bilirubin	X		X	X
ALT	X		X	X
Alk Phos	X	X	X	X
HCG**	X	X		
OSTEO ¹	X	X	X	X
BONE ALK ²	X	X	X	X
CTX ³	X	X	X	X
Pathology	X			

Nuclear scans: *bone scan required, Other imaging of indicator lesion(s): best study or studies for quantitative comparison after dose 3 and after dose 6 (e.g. LD of bone forming lesion on CT/MRI, or SUV on ¹⁸FDG-PET-CT, or SPECT with ^{99m}Tc-MDP bone scan, or Na¹⁸F PET).

[§]Brief Pain Survey.

⁺Evaluations to include anatomic imaging (CT or MRI) of all sites of disease along with chest CT at baseline and restaging for all patients will be done to allow for assessment of RECIST progression. RECIST progression will determine progressive disease regardless of other imaging.

HCG: Urine pregnancy test must be done within 7 days prior to start of study drug and when applicable prior to every cycle. Note serum HCG can be a false positive marker occasionally in osteosarcoma. For patients with a positive test result, pregnancy will be excluded by ultrasound.

**CBC w/diff: CBC every 2 weeks (± 7 days) for the first 2 cycles, then monthly or more frequently as clinically indicated

1 Osteoclastin

2 Bone specific alkaline phosphatase

3 Serum CTX

Timing of assessments

Assessments are to be done monthly as indicated in table 4.

7.1.2 Medical history

Medical history findings (i.e. previous diagnoses, diseases or surgeries) meeting all criteria listed below will be collected:

- Not pertaining to the study indication
- Start before signing of the informed consent
- Considered relevant to the study.

Detailed instructions on the differentiation between (i) medical history and (ii) adverse events can be found in Section 7.4.1.1.

7.2 Efficacy

Efficacy will be determined by

A) Trends comparing measurements of the indicator lesions using quantitative nuclear medicine scan will be used as exploratory end points. RECIST progression will determine progressive disease regardless of other imaging.

B) Alkaline phosphatase trends comparing before, after 3 doses and after 6 doses of Ra-223 dichloride

7.3 Pharmacokinetics / pharmacodynamics

7.4 Safety and Toxicity Monitoring

All subjects who receive at least one dose of study treatment will be valid for the safety analysis.

All observations pertinent to the safety of the study treatment will be recorded and included in the final report. Serious Adverse Events and/ any unexpected **and** clinically significant grade 3 or 4 toxicities will be reported to the MD Anderson IRB and Bayer. This trial will use the NCI-CTCAE v4.0 criteria for assessment of toxicity and SAE reporting with regard to toxicity grade.

7.4.1 Adverse events

Investigators should refer to the Safety Information section of the current IB for radium-223-dichloride, including the DCSI (development core safety information), for the expected side effects of Radium-223 dichloride. As with any agent, there is always the potential for unexpected AEs, including hypersensitivity reactions. The IB will be updated if any new relevant safety data are obtained.

All concomitant medications must be recorded in the subject's medical record at each clinic visit (ClinicStation) .

Subjects must be carefully monitored for AEs. This monitoring also includes clinical laboratory tests. Adverse events should be assessed in terms of their seriousness, intensity, and relationship to the study drug, or other chemotherapy/treatment.

